09-SEP-2020 / Amendment 3	Additional efficiency measures and treatment label for Adverse event summaries clarification	
Section 2.1 – Data analysis general information
 
Section 2.2.1 - Subgroup of interest
 
Section 2.3.2 – Demographics and other baseline characteristics
 
Section 2.4.2 – Prior & Concomitant medications
 
Section 2.8 – Other efficacy variables / exploratory analysis
 
Section 2.9 – Safety analyses
 
Section 2.9.1 – Adverse events
 
Section 2.9.1.1 – Adverse events of special interest / grouping of AEs
 
Section 5.13 – Health assessment questionnaire

01-May-2020 / Amendment 2	To refine derivation rules for Synovitis composite score and add	Section 2.3.2 – Demographics and other baseline characteristics

Date / version	Reason for update	Section and title impacted (Current)
	derivations for OMERACT (PDUS) enthesitis scores	Section 5.10 - OMERACT-EULAR Global PDUS OMERACT out of 48 joints Section 5.11 - OMERACT score of enthesitis
04-Mar-2020 / v2 (Amendment 1)	To incorporate updates made in Protocol Amendments 2 and 3 & during Dry run review	
Section 1 – Introduction
 
Section 1.1 – Study design
 
Section 1.2.3.1 – Sub-study objectives
 
Section 2.1 – Data analysis general information
 
Section 2.2.1 – Subgroup of interest
 
Section 2.3.2 – Demographics and other baseline characteristics
 
Section 2.4.1 – Study treatment/compliance
 
Section 2.4.2 – Prior & Concomitant medications
 
Section 2.5.4 – Supportive analysis
 
Section 2.6.1 – Key secondary endpoint
 
Section 2.6.3 – Handling of missing values/discontinuations
 
Section 2.6.4 – Supportive analysis
 
Section 2.7.1 – Secondary endpoint
 
Section 2.7.2 – Statistical hypothesis, model & method of analysis
 
Section 2.7.3 – Handling of missing values/discontinuations
 
Section 2.8 – Other efficacy variables / exploratory analysis
 
[REDACTED]
 
Section 2.9.1 – Adverse events

Date / version	Reason for update	Section and title impacted (Current)
		Section 2.9.1.1 – Adverse events of special interest / grouping of AEs
		Section 2.9.5 – Laboratory data
		Section 2.9.7.2 – Vital signs
		Section 2.10 – Pharmacokinetic endpoints
		Section 2.15 – Interim analysis
		Section 3.1 – Determination of sample size
		Section 4 – Change to protocol specified analyses
		Section 5.2 – AEs coding/grading
		Section 5.4 – Assessment windows

5.5.1	Primary analysis.....	52
5.5.2	Key secondary analysis.....	53
5.6	Rule of exclusion criteria of analysis sets	53
5.7	Power Doppler Ultrasonography.....	54
5.8	The classification criteria for psoriatic arthritis (CASPAR)	55
5.9	American College of Rheumatology measures and criteria of response.....	56
5.10	OMERACT-EULAR Global PDUS OMERACT out of 48 joints	57
5.11	OMERACT score of enthesitis.....	59
5.12	60
5.13	Health assessment questionnaire	61

5.14	PASI	62
	[REDACTED]	64
	[REDACTED]	65
	[REDACTED]	66
	[REDACTED]	66
6	References	68

List of abbreviations

ACR	American College of Rheumatology
AE	Adverse event
ANA	Antinuclear antibodies
ANCOVA	Analysis of covariance
ATC	Anatomical Therapeutic Chemical Classification
BMI	Body Mass Index
BSA	Body Surface Area
CASPAR	Classification Criteria for Psoriatic Arthritis
CHMP	Committee for Medicinal Products for Human Use
DBLK	Database Lock
DMARD	Disease Modifying Anti-Rheumatic Drug
FAS	Full Analysis Set
ECG	Electrocardiography
eCRF	Electronic Case Report Form
EULAR	European League Against Rheumatism
GLOESS	Global OMERACT-EULAR Synovitis Score
HAQ-DI	Health Assessment Questionnaire – disability index
IR	Inadequate response
JE	Joint Effusion
MAR	Missing at Random
MCAR	Missing Completely at Random
MCMC	Markov Chain Monte Carlo
MCP	Metacarpophalangeal
MedDRA	Medical Dictionary for Drug Regulatory Affairs
MMRM	Mixed Model Repeated Measures
MTP	Metatarsophalangeal
MTX	Methotrexate
OMERACT	Outcome Measures in Rheumatology
PASI	Psoriasis area and severity index
PD	Protocol Deviation
PDUS	Power doppler Ultrasound Sonography
PFS	Prefilled syringes
PK	Pharmacokinetics
PID	Distal interphalangeal
PIP	Proximal interphalangeal
PPD	Purified Protein Derivative
PsA	Psoriatic Arthritis

RF	Rheumatoid Factor
SAP	Statistical Analysis Plan
s.c.	Subcutaneous
SDI	Standard Disability Index
SH	Synovial Hyperplasia
SOC	System Organ Class
SpA	Spondyloarthritis
SJC	Swollen Joint Count
SPARCC	Spondyloarthritis Research Consortium of Canada
SRM	Standarized Response Mean
SSR	Sample Size Reestimation
TEAE	Treatment Emergent Adverse Events
TJC	Tender Joint Count
VAS	Visual Analogue Scale
[REDACTED]	[REDACTED]

1 Introduction

The purpose of this study is to provide early efficacy data using ultrasound on joint synovitis and enthesitis in addition to clinical efficacy already demonstrated in patients with active psoriatic arthritis (PsA) despite non-biologic DMARDs. This study is designed to leverage the sensitivity of Power Doppler ultrasonography available in clinical practice setting to better describe the time course of response to secukinumab (150 mg and 300 mg) on joint synovitis and enthesitis in PsA patients with an inadequate response to non-biologic DMARDs.

This document is based on the Clinical Study Protocol CAIN457A2354 v3 dated 27th November 2018. A Clinical Study Report will be prepared following the analysis outlined in this SAP.

1.1 Study design

This is a 52-week, multicenter, international study consisting of a 1 to 4-week Screening period, a 12-week randomized, placebo-controlled double-blind treatment period (Period 1), a 12-week open-label treatment period (Period 2) and a 6-month open-label extension period (Period 3), and a 12-week follow-up period after treatment completion.

Screening period

Eligible patients will be enrolled and enter a 1 to 4- week Screening period prior to randomization.

Treatment period 1 – placebo-controlled double-blind (Baseline to Week 12)

At Baseline, patients whose eligibility is confirmed will be randomized in 1:1 ratio in a double-blinded fashion to one of 2 treatment groups as follows:

- **Group 1:** secukinumab (150 mg s.c. or 300 mg s.c. depending on severity of skin lesions)
- **Group 2:** placebo

At each study treatment visit, all patients will receive 2 s.c. injections using PFSs since secukinumab is available in 1.0 mL PFSs. Patients assigned to secukinumab 150 mg will receive 1 PFS of secukinumab 150 mg and 1 PFS of placebo; patients assigned to secukinumab 300 mg will receive 2 PFS of secukinumab 150 mg; and patients assigned to placebo will receive 2 PFSs of placebo.

Primary analysis

The Week 12 analysis will be performed after all patients complete the Week 12 visit (see Section 2.15). Only the data analysts will be unblinded to the Treatment Period 1 randomization data after the Week 12 database lock/analyses. Summary results will be shared internally and externally; however, individual unblinded patient data will not be disclosed externally. The Ultrasonography Investigator and the Clinical Investigator will remain blinded from each other until the final database lock.

Treatment Period 2 – open-label treatment period (Week 12 to Week 24)

From **Week 12**, secukinumab will be given open-label to all patients irrespective of their initial treatment (i.e. only 150 mg or 300 mg secukinumab will be dispensed as 1 or 2 PFSs, respectively).

In **Group 1**, patients will continue to receive the same active dose of secukinumab every 4 weeks until Week 24 (i.e. at Week 12, 16 and 20); patients will no longer receive the placebo PFS, which was administered to maintain blinding.

In **Group 2**, patients will commence open-label secukinumab every 4 weeks from Week 12 until Week 24 (i.e. at Week 12, 16 and 20), based on their clinical characteristics (BSA or severity of skin lesions) at Week 12.

A blinded sample size estimation (SSR) will be performed when the first 60 patients have completed the Week 12 visit as described in Section 2.15.

Treatment Period 3 – extension period (Week 24 to Week 52)

Treatment Period 3 is an extension period to allow responder patients (if they wish and as per clinician's judgment) the possibility to continue open-label secukinumab treatment up to Week 52.

At Week 24, open-label secukinumab will continue to be assigned to patients in Group 1 and Group 2 at the same dose every 4 weeks until Week 52 at either the study site (i.e. Week 24, 36 and 52) or at home (Week 28, 32, 40, 44, 48).

At Week 24, patients who do not reach at least a 20% improvement in tender joint count (TJC) and swollen joint count (SJC) with secukinumab (150 mg or 300 mg) will be withdrawn from the study.

The Week 24 analysis will be performed after all patients complete the Week 24 visit (see Section 2.15).

The final analysis will be performed after the last patient has completed the Week 64/End of Study visit or early withdrawal visit (in case of early withdrawal of last patient from the study). After the final database lock and analyses have been completed, site personnel

(including the Ultrasonography Investigator and Clinical Investigator) will be unblinded to the original randomized treatment (sequence) assignment at randomization.

A follow-up visit is to be done 12 weeks after last study treatment administration for all patients, regardless of whether they complete the entire study as planned or discontinue prematurely. All AEs that occur during this post-treatment follow-up period will be included in the evaluation of treatment-emergent AEs.

The study population will consist of male and female patients aged ≥ 18 years with PsA as per the classification criteria for PsA (CASPAR) and with active PsA for at least 6 months and must have active disease as assessed by ≥ 3 tender joint count (TJC) out of 78 and ≥ 3 swollen joint count (SJC) out of 76 at Baseline and with an IR to non-biologic DMARDs and at least one clinical enthesitis at Screening and Baseline. Patients can be re-screened only once and 'no' re-screening study related procedures should be performed prior to written re-consent by the patient. Mis-randomized patients cannot be re-screened. The goal is to randomize 164 patients in total (82 patients per arm) at approximately 50 centers worldwide.

1.2 Study objectives and endpoints

1.2.1 Primary objective

To demonstrate that there is a difference between secukinumab and placebo in terms of joint synovitis response over 12 weeks as measured by the PDUS Global OMERACT-EULAR Synovitis Score (GLOESS) of the affected joints (out of 48 joints) in PsA patients with an inadequate response (IR) to non-biologic DMARDs.

1.2.2 Secondary objectives

1.2.2.1 Key secondary objectives

- To demonstrate that the efficacy of secukinumab at Week 12 is superior to placebo based on the proportion of patients achieving an ACR 20 response.
- To demonstrate that the efficacy of secukinumab at Week 12 is superior to placebo based on the proportion of patients achieving an ACR 50 response.
- To demonstrate that the clinical response of secukinumab at Week 12 is superior to placebo based on the change in SPARCC enthesitis index from Baseline to Week 12.

1.2.2.2 Other secondary objectives

- To evaluate the therapeutic effect of secukinumab versus placebo on joint synovitis from Baseline to Week 8 using the GLOESS score out of 48 joints

- To evaluate the therapeutic effect of secukinumab versus placebo on enthesitis at Week 12 using the OMERACT enthesitis score for each affected enthesis
- To evaluate the overall safety, tolerability and immunogenicity of secukinumab.

1.2.3 Exploratory objectives

- To explore the efficacy of secukinumab at Week 24, during the extension period, and other time points for assessments that are not part of the primary and secondary objectives as applicable only to:
 - ACR 20, ACR 50, ACR 70, ACR components, PASI 75, PASI 90, PASI 100,

1.2.3.1 Sub-study objectives

2 Statistical methods

2.1 Data analysis general information

The analysis outlined in this document will be performed by Novartis using SAS version 9.3 or higher software. All analyses outlined will also be performed by Novartis.

Comparative efficacy analyses (i.e. inferential efficacy comparisons with placebo) will focus on the time period when both active drug and the placebo are given in a manner suitable for making comparisons (e.g. double-blind). For AIN457F2354 this is the first 12-weeks of treatment. Comparative efficacy will be performed based on the FAS population using the randomized treatment. After week 12, the active secukinumab regimens will be compared using confidence intervals on the FAS population using treatment sequence. These treatment sequences represent the treatment combinations the subjects experience over the course of the entire trial in case of treatment switch at week 12.

The Week 3 efficacy assessment was removed from the study assessments in Protocol Amendment 2. Statistical comparisons at week 3 will not be presented due to the low number of subjects enrolled prior to this amendment.

Summary statistics for continuous variables will include N, mean, standard deviation, minimum, lower quartile, median, upper quartile and maximum values. Summary statistics for binary or discrete variables will be presented in contingency tables and will include absolute and relative frequencies.

The statistical analysis planned for the primary and secondary objectives are clearly stated, if not otherwise specified 95% confidence intervals may be presented along with point estimates and p-values will be presented as 1-sided.

Data analyses and summaries will be performed by treatment group (Secukinumab 150mg + 300 mg and Placebo) for baseline measurements, efficacy and safety data captured within the placebo-controlled period and for adverse events throughout the treatment periods.

Analyses of all efficacy and non-AE safety parameters for the treatment periods will be performed by treatment sequence and results presented for the following groups: secukinumab (150 mg + 300 mg), placebo – secukinumab (150 mg + 300 mg).

All listings will be presented by treatment sequence for efficacy and non-AE safety and by treatment for baseline and AE listings.

2.1.1 General definitions

Treatment periods

Period 1 = from first dose up to but not including Week 12 dose.

Period 2 = Week 12 dose up to but not including Week 24 dose.

Extension = Week 24 dose until Week 52.

Follow-up = After Week 52 until Week 64

Study Day 1 and other study days

The first day of administration of randomized study treatment (first dose) is defined as *Study Day 1 or Day 1*.

All other study days will be labeled relative to Day 1. For event dates on or after Day 1, study day for a particular event date is calculated as [Date of event] – [Date of first dose]+1, i.e., Day 2, Day 3, etc., will be one day, two days, etc., after Day 1, respectively. For the dates before Day 1, study day for an event date is calculated as [Date of event] – [Date of first dose], i.e., Day -1, Day -2, etc., will be one day, two days, etc., before Day 1, respectively. Duration of an event will be calculated as (Event end date – Event start date + 1).

The descriptor “Day 0” will not be used.

Screening, baseline and post-baseline definitions

Screening refers to any procedures (e.g., checking inclusion and exclusion criteria) performed prior to the date of first dose of study treatment. Per protocol, subject informed consent must be obtained prior to performing any study related activity. The date of signing informed consent is the start date of screening period. Any assessment

obtained during the screening period will be labeled screening assessment. Assessments made on Day 1 may occur before or after the randomization or the first dose.

For efficacy analyses, baseline is the last assessment (including unscheduled visits) obtained before the first dose of study treatment . All assessments obtained after the first dose of study treatment are considered as post-baseline unless otherwise specified.

For safety analyses, baseline is the last assessment (including unscheduled visits) obtained before the first dose of study treatment. All assessments obtained after the first dose of study treatment are considered as post-baseline unless otherwise specified.

Of note, re-randomization will not be used for baseline definition and only one baseline value will be defined referring to the first randomization.

Day of last dose of randomized study treatment

The date of last dose will be collected via the eCRF. The subject's exposure will be calculated considering the end of treatment period visit (e.g., treatment period 3 completion visit). If a subject discontinued early, then the last visit during the treatment period is considered (e.g. last visit in treatment period 2, if subject discontinued from treatment period 2).

2.2 Analysis sets

The following analysis sets will be used for the data analysis.

All screened patients : The all screened patients set will comprise all patients screened regardless of whether they were enrolled. Screen failures will be included.

Randomized set (RAN): The randomized set will be defined as all patients who were randomized.

Unless otherwise specified, mis-randomized patients will be excluded from the randomized set. Mis-randomized patients are defined as those patients who were mistakenly randomized prior to the site confirming all eligibility criteria had been met and to whom no study medication was given. Mis-randomized patients are treated as screen failures.

Full analysis set (FAS): The FAS will comprise all patients from the randomized set to whom study treatment has been assigned. Following the intent-to-treat principle, patients will be analyzed according to the treatment assigned at randomization.

Safety set (SS): The Safety set will include all patients who took at least 1 dose of study treatment during the treatment period. Patients will be evaluated according to study treatment received.

[REDACTED]

[REDACTED]

[REDACTED]

[REDACTED]

[REDACTED]

[REDACTED]

[REDACTED]

[REDACTED]

2.3 Patient disposition, demographics and other baseline characteristics

2.3.1 Patient disposition

The number of subjects screened will be presented. In addition, the reasons for screen failures will be provided. The number and percentage of subjects in the randomized set (who completed study periods) and who discontinued the study prematurely (including the reason for discontinuation) will be presented by study period for each treatment group and all subjects.

For each protocol deviation, the number and percentage of subjects for whom the deviation applies will be tabulated.

2.3.2 Demographics and other baseline characteristics

The following common background and demographic variables will be presented for the randomized set.

Continuous variables:

- Age (which is derived from date of birth and the screening assessment date)
- Height
- Weight
- Body mass index (BMI)

Body Mass Index (BMI) will be calculated using the following formula:

$$\text{BMI} = (\text{body weight in kilograms}) / (\text{height in meters})^2$$

For BMI, height and body weight used is the last value prior to first dose. If there is no weight recorded prior to taking of study treatment, BMI will be missing.

Categorical variables:

- Age categories (<65 years, 65 years and older, 75 years and older)
- Sex
- Race
- Ethnicity
- Source of patient referral
- Child bearing status
- Smoking status at baseline

Additionally the following psoriasis specific baseline characteristics and history of disease will be summarized:

- Baseline total BSA ($\leq 3\%$, $>3\%$)
- Baseline PASI
- Severity of psoriasis (CHMP guidelines, mild (total BSA $<10\%$ or PASI < 10), moderate ((PASI ≥ 10 or total BSA $\geq 10\%$) and PASI ≤ 20 and total BSA $\leq 20\%$), severe (total BSA $>20\%$ or PASI > 20))
- Moderate-to-severe Psoriasis (EMA criteria : total BSA $>10\%$ or PASI > 10 , FDA criteria : total BSA $\geq 10\%$ and PASI ≥ 12)
- CASPAR
- Global PDUS (GLOESS)
- SPARCC enthesitis index
- ACR components
- Time since diagnosis of psoriatic arthritis
- Time since diagnosis of psoriasis
- Previous exposure psoriasis therapies if applicable /PsA therapies
- QuantiFERON TV-Gold test or PPD skin test (depending on local guidelines)

- Distribution of patients by enthesitis severity at baseline; clinical enthesitis, Global and Total OMERACT enthesitis score at site level, number of enthesis involved per patient, and proportion of patients presenting with ultrasound OMERACT enthesitis >0 and its core components B Mode >0 and PD signal >0

- Proportion of PDUS (GS+ PD) synovitis by joint

Unless otherwise specified, summary statistics will be presented for continuous variables for all subjects in the FAS. Similarly the number and percentage of subjects in each category will be presented by treatment group for categorical variables for all subjects in the FAS.

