5.14 PASI

PASI scoring will be conducted during the study for all patients with a BSA $\geq 3\%$ at baseline and for patients with a BSA $\geq 3\%$ at subsequent visits (i.e. if not $\geq 3\%$ at baseline). The PASI assesses the extent of psoriasis on 4 body surface areas (head, trunk and upper and lower limbs) and the degree of plaque erythema, scaling and thickness. A PASI score ([Fredriksson and Pettersson 1978](#), [Weisman 2003](#), [Gottlieb 2005](#)) will be derived.

The head, trunk, upper limbs and lower limbs are assessed separately for erythema, thickening (plaque elevation, induration), and scaling (desquamation). The average degree of severity of each sign in each of the 4 body regions is assigned a score of 0-4. The area covered by lesions on each body region is estimated as a percentage of the total area of that particular body region. Further practical details help the assessment:

1. The neck is assessed as part of the head.
2. The axillae and groin are assessed as part of the trunk.
3. The buttocks are assessed as part of the lower limbs.
4. When scoring the severity of erythema, scales should not be removed.

Because the head and neck, upper limbs, trunk and lower limbs correspond to approximately 10%, 20%, 30% and 40% of the BSA, respectively, the PASI score is calculated using the formula:

$$\text{PASI} = 0.1(\text{EH}+\text{IH}+\text{DH})\text{AH} + 0.2(\text{EU}+\text{IU}+\text{DU})\text{AU} + 0.3(\text{ET}+\text{IT}+\text{DT})\text{AT} + 0.4(\text{EL}+\text{IL}+\text{DL})\text{AL}$$

The keys for the letters are provided in Table 12 below.

PASI scores can range from 0 corresponding to no signs of psoriasis to a theoretic maximum of 72.0.

T Psoriasis area and severity index scoring system

Body region	Erythema (E)	Thickening (plaque elevation, induration, I)	Scaling (desquamation, D)	Area score (based on true area %, A)*
Head (H) [†]	0 = none	0 = none	0 = none	0 = no involvement
	1 = slight	1 = slight	1 = slight	1 = >0-<10%
	2 = moderate	2 = moderate	2 = moderate	2 = 10-<30%
	3 = severe	3 = severe	3 = severe	3 = 30-<50%
	4 = very severe	4 = very severe	4 = very severe	4 = 50-<70%
				5 = 70-<90%
Trunk (T) [‡]	0 = none	0 = none	0 = none	6 = 90-100%
	1 = slight	1 = slight	1 = slight	0 = no involvement
	2 = moderate	2 = moderate	2 = moderate	1 = >0-<10%
	3 = severe	3 = severe	3 = severe	2 = 10-<30%
	4 = very severe	4 = very severe	4 = very severe	3 = 30-<50%
				4 = 50-<70%
Upper limbs (U)	0 = none	0 = none	0 = none	5 = 70-<90%

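### The mild psoriasis category in SAP section 2.3.2 overlaps moderate and severe, so the baseline severity counts depend on coding order

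*SAP*

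**What the plan says.** SAP section 2.3.2 lists the psoriasis-specific baseline characteristics. The severity bullet opens "Severity of psoriasis (CHMP guidelines, mild (total BSA", with a limit of below 10%, and continues "or PASI < 10), moderate ((PASI ≥ 10 or total BSA", with a limit of at least 10%. The moderate category is then capped by "and PASI ≤ 20 and total BSA", at most 20%. Severe is total BSA above 20% or PASI above 20.

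The next bullet gives a second classification, starting "Moderate-to-severe Psoriasis (EMA criteria : total BSA". Its EMA version is met by total BSA above 10% or PASI above 10, and its FDA version by total BSA of at least 10% together with PASI of at least 12.

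On reporting, the section states: "Similarly the number and percentage of subjects in each category will be presented by treatment group for categorical variables for all subjects in the FAS".

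Section 5.14 bears on the remedy: "PASI scoring will be conducted during the study for all patients with a BSA" of at least 3% at baseline, and for others once BSA reaches 3% at a later visit. A patient whose baseline BSA is below 3% may therefore have no baseline PASI.

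**The concern.** Mild, moderate and severe form an ordered scale, and a reader of a baseline table will take the levels as exclusive. As printed they are not. The moderate and severe rules are entered when *either* measure is high, while the mild rule is entered when *either* measure is low. Any patient whose two measures disagree about the threshold of 10 qualifies on both counts.

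Two programmers following this text could produce different tables. If mild is evaluated first, patients with moderate or severe values on one measure are reported as mild. If severe is evaluated first, they are not. If each level is counted separately, the percentages add to more than 100%. The first outcome would also set the severity line against the EMA line of the same table.

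**Working it through.** There is no figure in the plan to reproduce, so the check is logical. The inputs are the three rules in section 2.3.2 as printed, with B for total BSA (%) and P for PASI:

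- Mild: B < 10 or P < 10
- Moderate: (P ≥ 10 or B ≥ 10) and P ≤ 20 and B ≤ 20
- Severe: B > 20 or P > 20

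**Step 1: where the overlap lies.** Suppose one measure is below 10 and the other is at least 10. Mild is met through the lower measure. If the higher measure is at most 20, moderate is also met; if it is above 20, severe is also met. If both measures are below 10, only mild is met. If both are at least 10, mild is not met. Moderate and severe never coincide, because one requires both measures to be at most 20 and the other requires one of them to exceed 20.

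**Step 2: check on a grid.** The rules were applied to every combination of B from 0 to 100 in steps of 0.5 (201 values) and P from 0 to 72 in steps of 0.1 (721 values), which is 201 × 721 = 144,921 cells. Cell counts show the logic only; they do not estimate shares of patients.

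| Categories met | Mild with *or* (as printed) | Mild with *and* |
|---|---|---|
| Mild only | 2,000 | 2,000 |
| Mild and moderate | 4,120 | 0 |
| Mild and severe | 26,400 | 0 |
| Moderate only | 2,121 | 6,241 |
| Severe only | 110,280 | 136,680 |
| Total | 144,921 | 144,921 |

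The overlapping cells move intact: 2,121 + 4,120 = 6,241 and 110,280 + 26,400 = 136,680. No cell is unclassified under either version.

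**Step 3: can real PASI values fall in the overlap?** Use the formula and area scores in section 5.14. The region weights sum to 0.1 + 0.2 + 0.3 + 0.4 = 1, so with the same involvement in every region PASI is the sum of the three sign scores times the area score.

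- 12% involvement everywhere gives area score 2 (10 to <30%). Slight erythema, thickening and scaling give 1 + 1 + 1 = 3. PASI = 3 × 2 = 6. With B = 12 and P = 6 the patient is mild and moderate.
- 25% involvement everywhere also gives area score 2. Sign scores summing to 4 give PASI = 4 × 2 = 8. With B = 25 and P = 8 the patient is mild and severe.

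Widespread but low-grade lesions are enough; extreme scores are not needed.

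**Step 4: against the EMA line.** Any overlapping patient whose higher measure is above 10 meets the EMA moderate-to-severe definition while also meeting mild. Only a higher measure of exactly 10 escapes. The patient with B = 12 and P = 6 is a direct case.

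**Step 5: what each remedy does.** Excluding moderate and severe leaves exactly B < 10 and P < 10. For a patient with both measures, *mild with and* and *worst category met* therefore assign the same category. The grid gives every cell both values, so it says nothing about a patient with no baseline PASI. For that patient a strict *and* cannot be evaluated.

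**Step 6: size.** The document does not give the number of patients with discordant measures. With 82 planned per arm (section 3.1), each such patient shifts the mild percentage in that arm by 1/82 = 1.2 percentage points, depending on coding order.

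**The case against.** The best defence is that the printed *or* may serve a purpose. Section 5.14 does not require a PASI at baseline when BSA is below 3%, and the *or* lets such a patient be classed as mild on BSA alone. Simply replacing it with *and* could leave the patients with least skin disease unclassified. This stands, and it shapes the fix. It does not excuse the overlap for patients who have both measures.

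It is also fair that the document proves an overlap, not which wording was intended. The rule is attributed to CHMP guidelines, which are not reproduced, and a stated precedence would cure the problem with the *or* left in place. This too stands.

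A third defence is that the table does not rest on this line alone: baseline PASI, total BSA at the 3% cut and the EMA and FDA classifications are all in the same list. That limits the harm but does not make the severity row reproducible. The rule in section 5.4 for choosing the worst record does not help either, since it selects among several post-baseline assessments and not among categories met by one baseline assessment.

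A reader might infer more from the fact that section 1.1 makes the active dose depend on the severity of skin lesions, and conclude that the overlap affects dosing. The document does not support this: nowhere does it say that the mild, moderate and severe categories of section 2.3.2 determine dose. Nor does anything visible support an effect on the efficacy results, because the models in sections 2.5.2, 2.6.2, 2.7.2 and 5.5 do not contain the variable.

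**Conclusion.** The point holds as a defect in one descriptive baseline variable. As printed, every patient with one measure below 10 and the other at or above 10 belongs to two severity categories, no visible rule chooses between them, and the reported counts depend on programming order. Where the higher measure exceeds 10, reporting such a patient as mild also contradicts the EMA line of the same list.

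The importance is small. No visible estimate, test or p-value changes. The number of affected patients is unknown, so whether the table would shift noticeably cannot be said. Percentages above 100% are possible but need each level to be counted separately; misclassification through coding order is the likelier result. The conclusion rests on the internal logic of section 2.3.2 and on the visible text; whether redacted text uses the variable cannot be seen.

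**What to change.** Choose one of two wordings for the severity bullet in section 2.3.2:

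- Define mild as total BSA below 10% *and* PASI below 10, and state that patients with no baseline PASI because BSA is below 3% are classed on BSA alone; or
- Keep the printed limits and state that each patient is assigned to the worst category met, in the order severe, moderate, mild. A missing PASI should be treated as not meeting the moderate or severe limits.

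Either makes the categories exclusive and gives the same result for every patient with both measures. The cost is a sentence in the SAP and a few lines of code, with no new data and no change to any efficacy analysis.
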